3. STUDY DESIGN

In this pilot study we will evaluate the technical feasibility and clinical implementation of the Stroke Box in a small prospective cohort. After providing the Stroke Box to the patients, detailed information will be provided on the use of the Stroke Box and the patient will be helped with their first use.

The patient will use the Stroke Box to take at-home measurements for six months. Here we will be gathering data on blood pressure management, cardiac rhythm, patient engagement and have a user-based evaluation of the eHealth infrastructure. Patients will perform regular home measurements which the GP can use at the regular visits, and a nurse specialist in the LUMC will assess ECG measurements. We will keep close contact with both patient and GP to help in case of any questions. The patients will have access to the LUMC Box Support helpdesk who are an established customer service desk to help with any Box-related issues. We will ask the patients and GPs to contact us in case of any questions they might have. At the end of the pilot the user evaluation will be done through a questionnaire.

During the regular GP visits after the stroke related hospital admission, the GP and the nurse specialist will have insight in the collected data. We will evaluate the GP's experience of the data insight and technical usability using a questionnaire.

The study is estimated to take 12 months where we will have 6 months of inclusions and 6 months of follow-up.

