6.4 Summary of known and potential risks and benefits

Patients will have to measure their weight, temperature, blood pressure and heart rhythm on a regular basis. Regularly, they also will be asked questions about their general health. These activities may take some of their time.

A potential risk is that patients may be incorrectly assured that their data is monitored all the time by a trained physician. This might give them a false sense of security and hold them back from seeking medical assistance when this is required. To prevent this, we will

very clearly state in the patient information form (PIF) that this is not the case, and will make this integral part of the explanation when a patient starts with The Box.

A second potential risk is that patients may become alarmed by an incorrect detection of atrial fibrillation by the Withings Move ECG. Since it is not CE marked for AF detection, and given the results from a current validation study, we cannot exclude the occurrence of false positives or negatives. The smart watch and associated app give a warning when the measurement shows irregularities. It then either results in an “inconclusive” measurement or detects “atrial fibrillation”. It has been shown that this occurs when there are small irregularities in the hearth rhythm, such as atrial or ventricular extrasystoles or short pauses . The device then usually results in “inconclusive” but can also show “atrial fibrillation”. This can hence (incorrectly) distress the patient and cause him/her to seek unnecessary medical help. We will remedy this by clearly instructing the patient with what to do and who to contact in case of suspected AF.

After a measurement the Withings Move ECG performs a standard analysis resulting in either “normal”, “inconclusive” or “atrial fibrillation”. If their ECG smartwatch shows “atrial fibrillation” they are instructed to contact a dedicated nurse specialist who will check the measurements and refer them to the cardiology outpatient clinic if necessary. If the result is “inconclusive”, the patient is asked to repeat the measurement the next day. When the repeated measurement shows “inconclusive” again or when the measurement shows a warning for potential AF, they are instructed to also contact the dedicated nurse specialist who will contact the patient for further follow-up if necessary.

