When the patient records abnormal measurements indicating a high or rapid increase in blood pressure, they are instructed to not immediately contact a physician. This, in order to reduce the amount of (unnecessary) additional consults with the GP. Specifically, the patient is instructed to only contact their GP if they record a systolic blood pressure >140 mmHg for three days in a row or take up immediate contact if they record a systolic blood pressure >180 mmHg which is cause for immediate adjustment of the hypertension medication according to the NHG guidelines.

In addition to the standard care where patients receive a 48-hour Holter, patients who are suspected to have atrial fibrillation because of e.g. a cryptogenic stroke will be asked to also perform home measurements of their heart rhythm on a daily basis. They are recommended to do this on the same day and time every day. They will be very clearly instructed that their ECG measurements are not monitored regularly and that they should contact 112 in case of emergency.

After a measurement the Withings Move ECG performs a standard analysis resulting in either "normal", "inconclusive" or "atrial fibrillation". If their ECG smartwatch shows "atrial fibrillation" they are instructed to contact a dedicated nurse specialist who will check the measurements and refer them to the cardiology outpatient clinic if necessary. If the result is "inconclusive", the patient is asked to repeat the measurement the next day. When the repeated measurement shows "inconclusive" again or when the measurement shows a warning for potential AF, they are instructed to also contact the dedicated nurse specialist who will contact the patient for further follow-up if necessary. It should be noted that a clinical diagnosis will never be based on the self-measurements. Instead they serve as an early screening tool leading to patients with potential AF to be invited to the cardiology outpatient clinic to receive a diagnosis via the standard Holter measurement.

All ECG data are collected after the study and re-inspected by a PhD researcher of the LUMC for AF and in case of doubt checked again by an experienced cardiologist. In case of suspected AF, the patient is invited to the cardiology outpatient clinic. As 87% of stroke patients have ischemic strokes¹⁶ and about a

third of those have cryptogenic strokes, we expect to find cryptogenic strokes in about 29% of the LUMC stroke population.¹⁷

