Finally, the first ten patients with a modified Rankin Scale (mRS) ≥ 2 will receive access to the IkOefenZelf platform and will be asked to perform the practice modules on a regular basis.

Patients who smoke will also be asked to install the StopAdvisor app. This app will help them to quit smoking. The app is freely available from the IOS App Store and the Google Play Store.

Questionnaires

At the start and end of the study the patient will receive several questionnaires to evaluate their experiences with self-management, physical activity, healthy lifestyle intentions, their user experience, and their experience with eHealth. To evaluate the change in physical activity and lifestyle of the patient, they will be asked to fill out the SQUASH and HLI questionnaires at the start and end of the study. These questionnaires investigate respectively the amount of physical activity (e.g. sports) a patient has and what their intentions to a healthy lifestyle are (which includes questions on e.g. diet, smoking and alcohol use). In order to evaluate the experience of the patient with the self-management, they will be asked to fill out the PIH questionnaire at the start and the end of the pilot which measures how the patient manages his/her own disease. Finally, to evaluate the patient experience with the overall implementation of the Stroke Box, we will ask them to fill out the MAUQ questionnaire at the end of the study which includes questions on the technical ease-of-use, the general appearance and usefulness of the Stroke Box.

Moreover, we will evaluate the GP experience with the Stroke Box via the AIM, IAM and FIM²⁵ questionnaires for healthcare professionals which are four-item measures of implementation outcomes that are often considered “leading indicators” of implementation success.²⁶ An overview of the questionnaires used is given in the Table below.

Implementation will be assessed by the Reach Efficacy Adoption Implementation Maintenance (RE-AIM) model with a mixed model evaluation based on the normalization process theory.²¹⁻²³ The implementation will be evaluated from the perspective of the neurologists, GPs, practice assistant GP and patients.

Subject	Questionnaire	Estimated time
Physical activity	Short Questionnaire to Assess Health enhancing physical activity questionnaire (SQUASH) ²⁰	5 min
Healthy lifestyle intentions	Healthy lifestyle intentions questionnaire	4 min

Self-management	Partners In Health (PIH) questionnaire ¹⁸	4 min

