12.5 Temporary halt and (prematurely) end of study report

The investigator/sponsor will notify the accredited METC at the end of the study within a period of 8 weeks. The end of the study is defined as the last patient's last visit.

The sponsor will notify the METC immediately of a temporary halt of the study, including the reason for such an action.

In case the study is ended prematurely, the sponsor will notify the accredited METC within 15 days, including the reasons for the premature termination.

Within one year after the end of the study, the investigator/sponsor will submit a final study report with the results of the study, including any publications/abstracts of the study, to the accredited METC.

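### Section 8.3 places the review of all home ECGs after the study, so AF that the watch mislabels or the patient does not report could wait up to about 12 months for the intended clinic invitation

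*Combined protocol and SAP*

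**What the plan says.** Section 8.3 describes two routes by which a home ECG is read.

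- **During follow-up, at the patient's initiative.** If the watch shows AF, "they are instructed to contact a dedicated nurse specialist who will check the measurements". A second inconclusive result also leads to contact with the nurse. Section 6.4 repeats this route. On everything else patients are warned: "They will be very clearly instructed that their ECG measurements are not monitored regularly".
- **At the end, for everyone.** "All ECG data are collected after the study and re-inspected by a PhD researcher of the LUMC for AF". A cardiologist looks at doubtful tracings, and suspected AF leads to an invitation to the cardiology clinic.

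Section 3 says that "a nurse specialist in the LUMC will assess ECG measurements", with no timing and no statement of which recordings are meant. Section 3 also gives the GP and nurse specialist sight of the data around GP visits, and section 6.1 lets staff view measurements in the medical record. Sections 5.1 and 8.3 have the data sent to the hospital automatically.

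On timing, section 3 says: "The study is estimated to take 12 months where we will have 6 months of inclusions and 6 months of follow-up". Section 12.5 says: "The end of the study is defined as the last" patient's last visit. Yet section 8.3 also says: "At the start and end of the study the patient will receive several questionnaires", where the end must be the patient's own.

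**The concern.** Section 8.3 calls the recordings an early screening tool, and suspected AF at re-inspection triggers a clinic invitation. The review is therefore meant to lead to action, and its date matters to the patient.

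Two kinds of recording have no scheduled reader before that review. One is AF that the watch labels normal: section 6.4 says of the watch that "we cannot exclude the occurrence of false positives or negatives", and a normal label gives the patient no reason to call. The other is an AF or repeated inconclusive result that the patient does not report. Section 1 itself expects that stroke-related disability may reduce adaptation to self-monitoring.

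If the review waits for the last patient's last visit, the earliest patients wait longest, although their tracings are already at the hospital. What is at stake is a delayed referral for possible AF after a stroke or TIA.

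**Working it through.** **Inputs.** Inclusion 6 months, follow-up 6 months per patient, 12 months in all (section 3). End of study at the last patient's last visit (section 12.5).

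**Assumptions.** Inclusion time U1 and recording time within follow-up U2 are each uniform on 0 to 6 months. The patient reports no later alert, no one reads the tracing in between, and the review takes place on the earliest date its reading allows (the plan sets no deadline).

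**Wait for one unreported recording**

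| When the review takes place | Formula (months) | Mean | Maximum |
|---|---|---|---|
| Last patient's last visit, month 12 | 12 − U1 − U2 | 12 − 3 − 3 = 6 | 12 |
| Patient's own end | 6 − U2 | 6 − 3 = 3 | 6 |
| Proposed: within 4 weeks (0.92 month) of final recording | 6 − U2 + (0 to 0.92) | 3.0 to 3.9 | 6.0 to 6.9 |

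With review at month 12, P(wait > 6) = P(U1 + U2 < 6) = 0.50. The first patient included waits 12 − 3 = 9 months on average, the last 12 − 6 − 3 = 3.

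Against month 12, the proposed rule saves 6 − 3.9 = 2.1 to 6 − 3.0 = 3.0 months on average. It saves most for the first patient (up to 6 months) and nothing for the last. Against review at the patient's own end it saves no time; it only sets a deadline.

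**How many patients.** Section 4.4 expects two to three AF cases. With its inputs, cryptogenic strokes number 55 × 0.29 = 15.95, and AF cases 15.95 × 0.09 = 1.4 to 15.95 × 0.16 = 2.6. This is close to the stated figure, though the lower end rounds to one. The patients concerned here are those whose AF was recorded but mislabelled or unreported. The documents do not allow that number to be estimated; it may be zero.

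**Workload.** If 16 patients record daily for 26 weeks, there are 16 × 182 = 2,912 tracings. If the other 39 record weekly, as the Summary suggests, there are 39 × 26 = 1,014 more, or 3,926. Spread over months 6 to 12, this is 2,912/6 = 485 to 3,926/6 = 654 a month. At an assumed 0.5 to 1 minute each, that is about 4 to 11 hours a month.

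**The case against.** **The per-patient reading is well supported.** Section 8.3 uses the end of the study for the patient's own questionnaires, and the section 12.5 definition serves notification of the ethics committee. This stands: a reader might take 12 months as the plan's settled wait, and the text does not settle it. Section 12.5 nevertheless holds the only formal definition, and the section 8.3 phrase can be carried out either way.

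**Someone may look earlier.** The nurse specialist has an assessing role and access, and the word for the final review implies an earlier inspection. This stands in part. A reader might infer that no one at the hospital sees a home ECG until the end. The documents do not support that: reported results are checked, and other recordings may be viewed. But access is not a schedule, and for GPs section 8.3 lists blood pressure, weight and activity, not ECGs.

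**Patient-triggered review is deliberate and disclosed.** Patients are told that ECGs are not regularly monitored and to call 112 in an emergency. The standard 48-hour Holter remains, and no diagnosis rests on the watch. Watch and app both show an AF alert, patients with suspected AF record daily, and incapacitated adults and people who cannot use a smartphone are not enrolled. All this stands and limits the harm. It explains why there is no continuous surveillance, but not why a review that the plan already commits to has no date tied to the patient.

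**Conclusion.** The point holds as one about the timing of the final review. Under the section 12.5 definition, an unreported or mislabelled AF recording could wait up to about 12 months, and about 6 on average, before the invitation the protocol intends. Under the per-patient reading the wait is at most 6 months and 3 on average, and the only defect is an undefined phrase without a deadline. The figures rest on even inclusion and recording, no later reported alert and no informal reading in between; a later alert or an informal look would shorten them.

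Two stronger conclusions are not supported. A reader might infer that ECGs must be read at intervals during follow-up, but the documents make non-monitoring an open design choice, and interim reading has costs of its own. A reader might also infer a number of missed AF cases or harmed patients; the documents give no basis for one, and the total expected is only two to three.

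The change is worth making because it costs little and, under the formal definition, cuts the average wait from about 6 months to 3 to 4. It is a recommended improvement to patient safety, not a flaw that undermines the pilot.

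**What to change.** In section 8.3, replace the words that place the review after the study with a rule such as: *The PhD researcher re-inspects all ECGs of a patient within 4 weeks of that patient's final recording. Doubtful tracings go to the cardiologist, and a patient with suspected AF is invited to the clinic, at that time.* The 4-week limit is a proposal and has no source in the documents.

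In section 3, state which ECGs the nurse specialist assesses and when, in line with the patient-triggered route. Leave that route as it is, and record the dates of patient contact and of the re-inspection so that its yield can be measured.

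**Cost.** The same reader reads the same tracings, but spread over months 6 to 12, and the cardiologist must be available earlier. Because the reading follows the patient's own follow-up, the piloted pathway does not change.

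**Optional, not part of the required fix.** Readings every 4 weeks (weeks 4 to 28) would cut the average wait to (24 × 2 + 2 × 3)/26 = 2.1 weeks, with a maximum of 4. They would add a hospital-side step to the pathway under test and could feed the false sense of safety that section 11.4 warns about, so the patient information would have to say that they are not monitoring. That trade-off is for the sponsor.

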8.1.2 Secondary study parameters/endpoints

The secondary objectives of this study are:

- Gathering data on self-measured heart rhythm from the Withings Move ECG as an indicator of atrial fibrillation, weight and activity of patients using the Stroke Box, and performing a quality assessment of the collected data as assessed by regularity of assessments and frequency of occurrence of measurement error.
- The potential change in self-management of the patients due to the Stroke Box as measured through changes in lifestyle. This will be measured using changes in results from questionnaires on physical activity and healthy lifestyle intentions taken at the start and at the end of the study and the development of weight of the patient.

For the evaluation of physical activity we will adapt the Short Questionnaire to Assess Health enhancing physical activity questionnaire (SQUASH)²⁰, for the evaluation of healthy lifestyle intentions we will use the Healthy Lifestyle Intentions (HLI) questionnaire.

The evaluation of the self-management of the patient will be assessed by the Reach Efficacy Adoption Implementation Maintenance (RE-AIM) model with a mixed model evaluation based on the normalization process theory.²¹⁻²³

- Assessment of the patient adherence to the self-measurements and pharmacotherapeutic prophylactic therapy, using the Partners In Healthcare (PIH) questionnaire which measures how the patient manages his/her own disease. At the end of the study a comparison will be made between the group of patients who used the IkOefenZelf platform and those who did not.
- The technical implementation and patient adherence to the self-measurements by analysing how often they performed the measurements, if they experienced any problems as measured through the questions they asked during the study, and how they experienced the overall implementation as measured through the mHealth App Usability Questionnaire (MAUQ)²⁴ at the end of the study.
- User based evaluation of the technical – and workflow implementation for the GPs using the Stroke Box as evaluated with the Acceptability of Intervention Measure (AIM), Intervention Appropriateness Measure (IAM), and Feasibility of Intervention Measure (FIM)²⁵ questionnaires for healthcare professionals.

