8.1.3 Other study parameters

- Age
- Sex
- Body Mass Index
- Cardiovascular risk factors including medication (hypertension, diabetes mellitus, hypercholesterolemia, smoking, alcohol)
- Cardiovascular medical history (atrial fibrillation, stroke including all subtypes, heart failure, myocardial infarction)
- Stroke specific (stroke related disabilities as assessed by the National Institutes of Health Scale Score at discharge, modified Rankin Scale at discharge)
- The GP practice where the patient is registered and how the self-measurements are shared with the GP (i.e. via Medical Dashboard or manually)

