10. STATISTICAL ANALYSIS

10.1 Primary study parameter(s)

We will use descriptive statistics to assess blood pressure management, patient engagement and user-based evaluation of the eHealth infrastructure. We will analyze their self-measurement frequency of blood pressure, heart rhythm, weight, and activity using the mean measurements per week. The dropout rate will be described and the change in blood pressure in mmHg. This will be used as a basis for sample size calculation for future trials.

Moreover, we will use descriptive statistics to assess the clinical characteristics of our sample population.

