10.2 Secondary study parameter(s)

We will evaluate the change in lifestyle and user experience using qualitative questionnaires. Here we will make a quantitative comparison between questionnaires taken at the start and at the end of the study where we take into account the baseline characteristics of the patient, the type of stroke at hospital admission and whether the patient followed the IkOefenZelf modules as potential confounders.

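### Change in lifestyle is to be read from a questionnaire about intentions, with no end-of-study smoking or alcohol outcome and no specified analysis of change in weight or steps

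*Combined protocol and SAP*

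**What the plan says.** Section 8.1.2 defines a secondary parameter as "The potential change in self-management of the patients due to the Stroke Box as measured through changes in lifestyle". It names three sources. Two are questionnaires: "This will be measured using changes in results from questionnaires on physical activity and healthy lifestyle intentions", which are "taken at the start and at the end of the study and the development of weight of the patient". The end of that same sentence adds the third source, weight.

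Section 8.3 names the instruments: "To evaluate the change in physical activity and lifestyle of the patient, they will be asked to fill out the SQUASH and HLI questionnaires". It describes the HLI as asking "what their intentions to a healthy lifestyle are (which includes questions on e.g. diet, smoking and alcohol use". The questionnaire table in 8.3 also files it under intentions. Section 8.3 further asks patients who smoke to install the StopAdvisor cessation app.

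Section 8.1.3 lists, among other parameters, "Cardiovascular risk factors including medication (hypertension, diabetes mellitus, hypercholesterolemia, smoking, alcohol", without a time point.

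The analysis is in section 10. Section 10.1 states: "We will analyze their self-measurement frequency of blood pressure, heart rhythm, weight, and activity using the mean measurements per week". Section 10.2 states: "We will evaluate the change in lifestyle and user experience using qualitative questionnaires", and then plans a start-to-end comparison of those questionnaires.

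**The concern.** The quantity named is change in lifestyle, which is behaviour. For diet, smoking and alcohol, the instrument chosen to show it measures what patients intend. Intention and behaviour can move separately, so a start-to-end difference on the HLI does not show that anyone smoked less, drank less or ate differently. A report written from section 10.2 could nevertheless present it under that label.

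The study also collects data closer to behaviour and gives them no role in assessing change. Weight is named as a source in 8.1.2 but is missing from 10.2. Steps are uploaded automatically, and 8.3 itself classes measured weight and activity as lifestyle data for the GP. Even so, section 10 counts only how often they arrive. Change in physical activity therefore depends on patients' own reports, in an unblinded study (section 8.2).

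What is at stake is whether the pilot can answer its own lifestyle objective. Section 11.4 offers improved lifestyle as a potential benefit of taking part, so a result under that name will be read as behaviour.

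**Working it through.** The plan gives no figure for lifestyle change, quitting or steps, so there is none to reproduce. The check is mainly a comparison of sections, followed by an illustration of the precision a fix could offer.

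**Step 1. Trace each component from endpoint to analysis.**

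| Component | Collected at start and end? | Analysis of change specified? |
|---|---|---|
| Diet, smoking and alcohol: intentions | Yes, HLI (8.1.2, 8.3) | Yes, questionnaire comparison (10.2) |
| Smoking and alcohol: actual status | Listed in 8.1.3, no time point | No |
| Quitting among smokers | Not specified | No |
| Physical activity: self-report | Yes, SQUASH (8.1.2, 8.3) | Yes (10.2) |
| Physical activity: steps | Through follow-up when the watch is worn (8.3) | No, frequency only (10.1) |
| Weight | Weekly (8.3); named as a source (8.1.2) | No; 10.1 gives frequency, 10.2 omits it |

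The other start-and-end questionnaire for patients, the PIH, concerns how patients manage their disease. It does not fill the gap. Section 10.1 adds that clinical characteristics are described for the sample, which gives smoking and alcohol no role as outcomes.

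**Step 2. How precise would a quit count be?** The sample size of 55 is from section 4.4. The documents give no smoking prevalence and no quit rate. I assume 15%, 25% or 35% smokers and about 30% quitting. Smokers = 55 × prevalence, rounded; quitters = 0.30 × smokers, rounded.

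- 15%: 55 × 0.15 = 8.25, so 8 smokers; 2 quit (25%); 95% Wilson interval 7% to 59%.
- 25%: 55 × 0.25 = 13.75, so 14 smokers; 4 quit (29%); interval 12% to 55%.
- 35%: 55 × 0.35 = 19.25, so 19 smokers; 6 quit (32%); interval 15% to 54%.

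The Wilson limits are [p + z²/2n ± z√(p(1−p)/n + z²/4n²)] / (1 + z²/n), with z = 1.96. For n = 8 and p = 0.25 the centre is (0.25 + 0.240)/1.480 = 0.331 and the half-width is 0.260, which gives 0.07 to 0.59.

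Such a result can be described but not tested.

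**Step 3. How precise would mean change in steps or weight be?** The half-width of a 95% interval, in units of the standard deviation of change, is 1.96/√n. With n = 55 it is 0.26. With 20% missing (assumed), n = 44 and it is 0.30. That is adequate for description.

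**Step 4. What baseline do steps have?** The watch comes with the Box, so there is no step record before the Box. Only early-versus-late change within follow-up is available, and the early weeks at home overlap recovery from the stroke.

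**The case against.** The best defence is that the protocol is open about what it measures. Sections 8.1.2 and 8.3 both label the HLI as intentions. Smoking cessation is not among the objectives in section 2, and section 6.1 offers StopAdvisor to smokers who are interested. A quit count from a handful of smokers with no comparator says little. Early-to-late steps mix recovery with lifestyle, and the SQUASH baseline is taken at the start of the study, so the two changes do not share a starting point. All of this concerns a secondary, descriptive objective.

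Much of that stands, and it limits the point to a low-cost improvement. It does not remove the mismatch: 8.1.2, 8.3 and 10.2 all name change in lifestyle as the thing evaluated, not change in intentions alone.

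The documents do not support several stronger inferences that a reader might draw:

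- *Quitting is never measured.* Section 8.1.3 lists smoking without timing, and the HLI contains smoking questions whose wording is not shown. What can be said is that no quit outcome or end-of-study status is specified.
- *Lifestyle change rests on questionnaires alone.* This is true of section 10.2 but not of 8.1.2, which includes weight.
- *The step data are ignored.* The Summary says activity data will be gathered and evaluated. What is missing is a method for assessing change.
- *A successful quitter's HLI score would stay flat or fall, or scores would start near the maximum.* Either would depend on items and scoring that the documents do not give.
- *A weak activity measure will be carried into the future trial.* That trial is described as concerning hypertension management and AF detection; activity is not named as an outcome.

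**Conclusion.** The point holds as a gap between the construct named and the measures analysed. For diet, smoking and alcohol, the only scheduled start-and-end lifestyle instrument is one the protocol says measures intentions. Weight drops out between 8.1.2 and 10.2, and steps have no specified analysis of change.

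The consequence is a risk of mislabelled or uninformative lifestyle results. The primary blood pressure parameter and the sample size are untouched. The conclusion rests on the text alone; the smoker, quit and missing-data figures are assumptions used only to show precision. It is worth correcting because the remedy is cheap and mostly uses data already planned.

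**What to change.** 1. In 8.1.3 and 8.3, state that current smoking status and alcohol use are recorded at both start and six months. In 10.2, report the number who quit among baseline smokers and the change in alcohol use, descriptively and with intervals. Report the HLI as change in intentions, not as change in lifestyle.
2. In 10.2, add change in weight, and change in mean daily steps on days the watch was worn, from the first four weeks at home to the last four weeks. Define a worn day in advance. Show these beside the SQUASH change. State that the early period is already on the Box and overlaps stroke recovery, so the comparison is descriptive and is not a comparison with life before the Box.

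The cost is two short items and one descriptive analysis of data already uploaded, with no new device and no effect on sample size. The drawbacks are few smokers (a number the documents do not give), wide intervals, and missing steps when the watch is not worn.
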